8.4.1.4 HiSCR₅₀, HiSCR₇₅, HiSCR₉₀, and HiSCR₁₀₀ among Week 16 Responders

See Section 8.4.1.1 for the derivation of HiSCR response.

Summaries of HiSCR₅₀, HiSCR₇₅, HiSCR₉₀, and HiSCR₁₀₀ responders at each visit from Week 16 through Week 48 will be summarized based on a subset of participants in the MS who achieve response at Week 16. The summaries will be as follows:

- HiSCR₅₀ responder rate based on participants who achieved HiSCR₅₀ response at Week 16
- HiSCR₇₅ responder rate based on participants who achieved HiSCR₇₅ response at Week 16
- HiSCR₉₀ responder rate based on participants who achieved HiSCR₉₀ response at Week 16
- HiSCR₁₀₀ responder rate based on participants who achieved HiSCR₁₀₀ response at Week 16

Line plots of the above HiSCR responder rate categories over time (from Week 16 to Week 48), by treatment group, will be produced.

8.4.1.5 Time to loss of response of HiSCR₅₀, HiSCR₇₅, HiSCR₉₀, and HiSCR₁₀₀ in Week 16 responders

See Section 8.4.1.1 for the derivation of HiSCR response.

Time to loss of response will be based on the MS and include only participants who had the corresponding HiSCR response at Week 16 (considering intercurrent event handling from the composite estimand described in Section 8.2.2).

Time to loss of response of HiSCR₅₀, HiSCR₇₅, HiSCR₉₀, and HiSCR₁₀₀ (in days) is defined as: Date of loss of response of HiSCR₅₀, HiSCR₇₅, HiSCR₉₀, and HiSCR₁₀₀ - Date of Week 16 treatment administration + 1.

Time to loss of response will be estimated and presented using the Kaplan-Meier product-limit method for each treatment. Participants who experience an intercurrent event prior to loss of response will be considered as having lost response on the date of intercurrent event. Participants who reach the Week 48 Visit without loss of response will be censored at the date of the Week 48 Visit. Participants who discontinue treatment or study, for reasons other than those already defined for an intercurrent event, and who have not yet displayed loss of response by the time of withdrawal, will be censored at the date of the last lesion count assessment.

8.4.1.6 Partial response

See Section 8.2.1 for the derivation of AN count.

A partial response is defined as a $\geq 25\%$ reduction in AN count from Baseline (Week 0) at a particular timepoint.

The number and percentage of participants who are partial responders at Week 16 and become HiSCR₅₀, HiSCR₇₅, HiSCR₉₀, and HiSCR₁₀₀ responders in the Maintenance Treatment Period will be summarized by treatment group and visit. These analyses will be based on the subset of participants in the MS that are partial responders but not HiSCR₅₀, HiSCR₇₅, HiSCR₉₀, and HiSCR₁₀₀ responders, respectively, at Week 16. These summaries will be based on observed case data and will not consider the occurrence of intercurrent events.

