2.3 Study design and conduct

2.3.1 Study description

HS0004 is a Phase 3, randomized, double-blind, placebo-controlled, multicenter, pivotal study evaluating the efficacy and safety of bimekizumab in study participants with moderate to severe HS. Study participants meeting the inclusion criteria who do not meet any exclusion criteria will complete a Screening Period of 14 days to up to 5 weeks; a double-blind, 48-week Treatment Period comprising a 16-week Initial Treatment Period and 32-week Maintenance Treatment Period; and a 20-week Safety Follow-up (SFU) Period following the final injection of investigational medicinal product (IMP) if study participants do not enter a subsequent extension study (HS0005) or withdraw prematurely from treatment.

Study participants will be randomized in a 2:2:2:1 ratio (stratified by Hurley Stage and current antibiotic use) to 1 of 3 dose regimens of bimekizumab or placebo as shown in the schematic (Figure 2-1).

Figure 2-1: Study Schematic

HiSCR₅₀=a 50% reduction in the total abscess and inflammatory nodule count with no increase from Baseline in abscess or draining tunnel count;

IMP=investigational medicinal product; [REDACTED]

*Week 16 = primary endpoint (HiSCR₅₀ bimekizumab versus placebo)

a Study participant should discontinue from the study from Week 32 on if no partial response is achieved (partial response is defined as $\geq 25\%$ improvement in abscess and inflammatory nodule count relative to Baseline [Week 0] lesion values.)

b Study participants achieving an improvement of at least 25 % in abscess and inflammatory nodule count continue in HS0005 (Extension Study).

c 20-week Safety Follow-up (from last IMP injection) for any study participant who discontinues from study prior to Week 48, or who does not continue in HS0005.

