3 DATA ANALYSIS CONSIDERATIONS

3.1 General presentation of summaries and analyses

Statistical analysis and generation of tables, figures, study participants data listings, and statistical output will be performed using SAS Version 9.4 or higher. All tables and listings will use Courier New font size 9.

Descriptive statistics will be displayed to provide an overview of the study results. For continuous variables, descriptive statistics will include number of study participants with available measurements (n), mean, standard deviation (SD), median, minimum, and maximum.

For PRO continuous variables, descriptive statistics will also include variable score, absolute and percentage changes from baseline, Q1 and Q3, 10th, and 90th percentiles.

If no participants have data at a given time point, then only n=0 will be presented. The other descriptive statistics will be left blank. If $n < 3$ then the n, minimum, and maximum only will be presented. The other descriptive statistics will be left blank. If $n = 3$ n, mean, median, minimum and maximum will be presented only. The other descriptive statistics will be left blank.

For categorical variables, the number and percentage of study participants in each category will be presented. Unless otherwise noted, the denominator for percentages will be based on the number of study participants included in the respective analysis set. Study participants with missing data will be accounted for using the following approaches:

- For summaries of demographics and Baseline characteristics: percentages will be based on all study participants in the analysis set and a “Missing” category (corresponding to study participants with missing data for the variable being summarized) will be included as the last row in the list of categories being summarized.
- For summaries of efficacy and safety endpoints, unless otherwise specified: percentages will be based only on those study participants with observed data for the variable being summarized. As the denominator may be different from the number of study participants in the analysis set being considered, the denominator will be displayed in the table. The general format for displaying this will be “n/Nsub (%)”.

Percentages will be presented to 1 decimal place. If the percentage is 100%, a decimal will not be presented. If the count is 0, the percentage will not be presented. Typically, the % sign will be presented in the column header, but not with each individual value.

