4.2.1.3 Handling missing data for the other efficacy endpoints

For other binary efficacy endpoints, missing data will be imputed using the same method as the primary efficacy endpoint. NRI and OC methods will be performed as sensitivity analyses of HiSCR₅₀, HiSCR₇₅, HiSCR₉₀, and HiSCR₁₀₀.

For other continuous efficacy endpoints, the MI-MCMC/monotone regression method will be used to impute missing data as the primary method, regardless of whether the missing data are preceded by an intercurrent event. That is, if an intercurrent event occurs on or before a visit, the result for that visit will be treated as missing and imputed with the missing data. If the imputation model cannot converge, LOCF will be used.

For other ordinal endpoints (EQ-5D-3L, PGI-S-HS, PGI-C-HS, PGI-S-SP, PGI-C-SP), the OC method will be applied as the primary analysis method. No imputation is applied.

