4.2.1.4 Missing Data Overview and Summary

In summary, the approaches listed below will be used in this study for handling missing data for efficacy endpoints as appropriate:

- **NRI:** Participants who have missing data at the timepoint of interest are treated as though they did not respond to the treatment. This approach is also referred to as Composite Estimand (NRI).
- **Multiple Imputation (MI) – MCMC / Monotone Regression:** Using multiple imputation methodology, intermittent missing data are imputed based on the MCMC method, and monotone missing data are imputed using monotone regression.
- **MI–MCMC / Reference-based imputation:** Using multiple imputation methodology, intermittent missing data are imputed based on the MCMC method, and monotone missing data are imputed using an imputation model based on placebo (reference) data.
- **LOCF:** Post-Baseline missing data are imputed by carrying forward the last available observation (including Baseline).
- **Tipping point analyses:** Assumptions will be made about average outcomes among the subsets of participants who prematurely discontinued study treatment. Various “delta adjustments” will be made to the assumed responses among missing data in each treatment arm with varying degrees of plausibility in order to identify assumptions about the missing

data under which the conclusions change (O’Kelly, 2014). Then, the plausibility of such assumptions is discussed.

- **Observed case (OC):** Missing data are not imputed. Only participants with available data who have not discontinued study treatment at the given timepoint are considered. Study participants with missing data or who have prematurely discontinued study treatment will be treated as missing.

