Kaplan-Meier plots of time to HiSCR responses will be presented by treatment group. In these Kaplan-Meier plots, the line will start at 0 (since there are no responders at Week 0) and will increase over time, representing time to achieving the response.

The median time to response, including the 2-sided 95% confidence interval, will be calculated for each treatment.

8.4.1.3 HiSCR₂₅, HiSCR₅₀, HiSCR₇₅, HiSCR₉₀, and HiSCR₁₀₀ response at both Weeks 16 and 48

See Section 8.4.1.1 for the derivation of HiSCR response.

The number and percentage of HiSCR₂₅, HiSCR₅₀, HiSCR₇₅, HiSCR₉₀, and HiSCR₁₀₀ responders at both Weeks 16 and 48 will be summarized based on the RS and MS.

Missing data for the above summaries will be handled using NRI. That is, participants are counted as responders only if they have an observed HiSCR at both Weeks 16 and 48 and have no intercurrent events through Week 48. Otherwise, they are treated as not responding.

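### Section 8.4.1.6 reports progression of Week 16 partial responders on observed cases only, which raises the rate at visits after nonresponders have left; no composite or imputed version is planned

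*SAP*

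**What the plan says.** Section 8.4.1.6 defines partial response as a "reduction in AN count from Baseline (Week 0) at a particular timepoint" of at least 25%. It then asks how many Week 16 partial responders become HiSCR50, 75, 90 or 100 responders in the Maintenance Treatment Period, by treatment group and visit. The starting subset is fixed at Week 16: "These analyses will be based on the subset of participants in the MS that are partial responders but not" yet responders at the HiSCR level of that table. On data handling it says: "These summaries will be based on observed case data and will not consider the occurrence of intercurrent events".

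Four other places bear on what this produces.

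- Section 4.2.1.4 defines observed case: "Only participants with available data who have not discontinued study treatment at the given timepoint are considered".
- Section 3.1 sets the default denominator for efficacy summaries: "percentages will be based only on those study participants with observed data for the variable being summarized".
- Section 2.3.1, Figure 2-1, footnote a: "Study participant should discontinue from the study from Week 32 on if no partial response is achieved".
- Section 4.2.1.3 gives the general rule: "For other binary efficacy endpoints, missing data will be imputed using the same method as the primary efficacy endpoint". Under Section 4.2.1.1 that method sets intercurrent events to nonresponse and handles the remaining missing data by multiple imputation.

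The neighbouring endpoint in Section 8.4.1.3, response at both Weeks 16 and 48, uses nonresponder imputation (NRI). Participants there are "counted as responders only if they have an observed HiSCR at both Weeks 16 and 48 and have no intercurrent events through Week 48".

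**The concern.** The question is what becomes of people who had a partial response at Week 16. Answering it needs the Week 16 group to stay whole. Under the observed-case rule the group does not stay whole: a participant who loses partial response and leaves under the Week 32 rule disappears from later visits. The exit is caused by the outcome being summarised, so the remaining denominator is selected on that outcome.

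The second clause of the sentence acts in the same direction. A participant who reaches HiSCR after starting rescue antibiotics, and stays on study treatment, counts as having progressed. The SAP's composite rule would call that nonresponse.

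At stake is a descriptive rate that could be cited to say that partial responders gain from continued treatment. This table is the only planned summary of that subset, and it has no composite, NRI or multiply imputed counterpart.

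**Working it through.** The SAP states no rate, dropout or subset size for this endpoint, so there is no figure to reproduce. The direction can be derived; the size can only be illustrated.

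**Step 1: who the Week 32 rule removes.** Partial response needs at least a 25% AN reduction. HiSCR50, 75, 90 and 100 need at least 50%, 75%, 90% and 100% (Sections 8.2.1 and 8.4.1.1). Anyone below 25% therefore fails all four at that visit, and everyone removed by the rule is a nonresponder when removed.

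**Step 2: effect on the rate.** Let r be the share of the fixed Week 16 subset in response at a visit without an intercurrent event, and d the share gone by then as nonresponders.

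- Fixed denominator, exits counted as not progressed: r
- Observed case: r/(1-d), which exceeds r whenever r > 0 and d > 0

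**Step 3: illustration.** All values of r and d are assumed.

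| r | d = 5% | d = 10% | d = 20% | d = 30% |
|---|---|---|---|---|
| 30% | 31.6% | 33.3% | 37.5% | 42.9% |
| 40% | 42.1% | 44.4% | 50.0% | 57.1% |
| 50% | 52.6% | 55.6% | 62.5% | 71.4% |

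For example, 30 of 100 becomes 30 of 80, or 37.5%.

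**Step 4: rescue antibiotics.** Let a further share a of the subset be observed responders only after rescue. The observed-case rate is then (r + a)/(1-d), while the composite rate stays at r. With a = 5% (assumed), r = 30% and d = 20%, this is 0.35/0.80 = 43.75% against 30%.

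**Step 5: differences between regimens.** The direction depends on how d differs by arm.

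- Equal loss, d = 20% in both arms: 50% and 30% become 62.5% and 37.5%. The gap widens from 20 to 25 points.
- Unequal loss: 50% with d = 10% becomes 55.6%, and 40% with d = 30% becomes 57.1%. The order reverses.

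**Step 6: when it applies.** The table is by visit. A participant who is below 25% at Week 32 and still on treatment is an observed nonresponder at Week 32. The Week 32 rule distorts only the visits after exit. Before Week 32, the same effect can come only from other discontinuations of nonresponders.

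**Step 7: whether the rule is fully specified.** Section 4.2.1.4 excludes participants who have stopped study treatment. Section 3.2.2 maps a premature end of treatment (PEOT) assessment made after a scheduled visit to the next scheduled visit and treats it as observed there. Section 8.4.1.6 disregards intercurrent events, and stopping treatment for an adverse event or lack of efficacy is one of them (Section 3.9). Whether off-treatment and mapped PEOT assessments enter this table is therefore open, and two programmers could differ.

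**The case against.** **The rule is explicit.** Section 8.4.1.6 is a specific exception to Section 4.2.1.3, and the amendment record in Section 13.1 shows that the sentence was added on purpose. Section 8.4.1.3 also departs from the general rule, by using NRI. Other descriptive endpoints use observed-case denominators (Sections 8.4.2.2, 8.4.3 and 8.4.6). All of this stands, so the point is a poorly chosen exception and not a contradiction. It does not remove the selection. Table 4-1 does list observed case for other responder endpoints, but footnote d makes it a sensitivity analysis beside the imputed one, and here there is no imputed one.

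**The shrinking denominator will be visible.** Section 3.1 requires n/Nsub to be shown. That reveals the loss but not that those lost were failures. The alternative handlings in Section 8.4.1.1 cover the by-visit HiSCR summaries but not this subset.

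**The footnote may not reach this group.** It does not say how loss of an earlier partial response is treated, and the SAP alone does not settle this. The reading used here, that status is judged at the visit, fits the timepoint-specific definition in Section 8.4.1.6 but remains an assumption.

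**This subset is sheltered from the rule.** A reader might infer that outcome-driven removal affects this endpoint more than any other. The SAP does not support that. The subset starts with partial response, so those most exposed are excluded. The HiSCR75, 90 and 100 tables also include existing HiSCR50 responders, who would have to fall from at least 50% to below 25% to be caught.

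**Conclusion.** The point holds as a matter of direction. At visits after exit, removing nonresponders gives r/(1-d) in place of r, and counting responses after rescue antibiotics adds to it. Both raise the reported rate relative to the composite or NRI rate on the fixed Week 16 subset. Against a multiply imputed rate, observed case is too high if those who left would have progressed less often than those who stayed. That is likely, since they were selected for failing.

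The conclusion assumes that footnote a covers participants who have lost an earlier partial response and that data after discontinuation are excluded as Section 4.2.1.4 says. The size cannot be computed from the documents; every percentage above is illustrative.

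A reader might also infer that the rule shrinks differences between maintenance regimens. Step 5 shows that it can widen, narrow or reverse them, and the SAP gives nothing on loss by arm to decide which.

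This is a descriptive endpoint outside the testing sequence in Section 4.5 and absent from the nominal p-value list in Section 8.5. No confirmatory test or type I error is affected. It is a worthwhile, inexpensive correction.

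**What to change.** Replace the last sentence of Section 8.4.1.6 so that the main summary works as follows.

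- **Denominator:** all Maintenance Set participants who, on observed Week 16 data, had a partial response and had not reached the HiSCR level of that table. It stays the same at every later visit.
- **Not progressed, at that visit and later ones:** anyone with an intercurrent event, and anyone who left under the Week 32 partial-response rule, whatever reason is recorded. Otherwise an exit coded under another reason would be imputed from those who stayed.
- **Other missing data:** the Section 4.2.1.3 method, or NRI as in Section 8.4.1.3. Name one.
- **Observed-case table:** keep it as supportive with n/Nsub, and state whether off-treatment and mapped PEOT assessments count.

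The discontinuation rule itself is untouched and no new data are needed. The cost is a rewritten sentence, some programming and somewhat lower reported rates. If NRI is chosen, there is some downward bias, because participants missing for unrelated reasons, including some already in response, count as not progressed.

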8.4.2 Lesion count

8.4.2.1 Change from Baseline in lesion count

At each visit, lesion counts will be summarized by treatment group, anatomical region, and lesion type. The following lesion types will be summarized:

- Abscesses
- Inflammatory nodules
- ANs
- Non-inflammatory nodules
- Draining tunnels (fistulas/sinus tracts)
- Non-draining tunnels (fistulas/sinus tracts)
- HS scars

Total lesion counts (ie, the total across all anatomical regions) will be summarized by visit and lesion type, treatment group, overall and by Baseline Hurley Stage. Summaries will also be presented for the change and percentage change from Baseline in lesion counts by anatomical region and total lesion counts by lesion type.

A line plot of the percentage change from Baseline in AN count over time by treatment group will be produced. Separate plots will also be produced for the percentage change from Baseline

in the abscess count, inflammatory nodules count, and draining tunnel count, respectively, over time.

In order to investigate the effect of intercurrent events and missing data handling on lesion count data, the following **additional** iterations of each of the aforementioned plots (percentage change in AN count, abscess count, inflammatory nodule count and draining tunnel count, respectively) will be presented, with corresponding summary statistics tables:

- Intercurrent events:
 - Participants who have experienced intercurrent events
 - Participants who have not experienced intercurrent events
- Missing data handling:
 - Observed lesion counts (i.e., non-imputation)
 - Imputed lesion counts

Lesion count data will be listed by treatment group and anatomical region and will show region-specific Hurley Stage and worst overall Hurley Stage for each participant and visit. The total count for each type of lesion, across all anatomical regions at each visit will be listed separately. For the total abscess count and total draining tunnel (fistula/sinus tract) count, the change from Baseline will be listed; for the AN count, the percentage change from Baseline will be listed.

8.4.2.2 AN count of 0, 1, or 2

The number and percentage of participants with an AN count of 0, 1, or 2 will be presented by treatment group and visit. The denominator for the percentage calculations will be the number of participants in each treatment group in the RS with non-missing data at each visit.

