2.2.1.3 Other efficacy endpoints

The other efficacy endpoints are defined as:

- Time to response of HiSCR₂₅, HiSCR₅₀, HiSCR₇₅, HiSCR₉₀, and HiSCR₁₀₀
- HiSCR₂₅, HiSCR₅₀, HiSCR₇₅, HiSCR₉₀, and HiSCR₁₀₀
- Absolute change from Baseline in International Hidradenitis Suppurativa Severity Score System (IHS4)
- Change from Baseline in the HS-Physician’s Global Assessment 6-point scale
- Absolute and percentage change from Baseline in high-sensitivity C-reactive protein (hs-CRP)
- Initiation of systemic antibiotic rescue therapy
- HiSCR₂₅, HiSCR₅₀, HiSCR₇₅, HiSCR₉₀, and HiSCR₁₀₀ at both Weeks 16 and 48
- Time to loss of response of HiSCR₅₀, HiSCR₇₅, HiSCR₉₀, and HiSCR₁₀₀ in Week 16 responders
- Partial responders (defined as a $\geq 25\%$ reduction in AN count from Baseline [Week 0]) at Week 16 who progress to HiSCR₅₀ during the Maintenance Treatment Period

- Partial responders (defined as a $\geq 25\%$ reduction in AN count from Baseline [Week 0]) at Week 16 who progress to HiSCR₇₅, HiSCR₉₀, and HiSCR₁₀₀ response during the Maintenance Treatment Period
- Change and percentage change from Baseline in lesion counts (abscess count, inflammatory nodule count, AN count, and draining tunnel count)
- AN count of 0, 1, or 2
- AN₂₅, AN₅₀, AN₇₅, AN₉₀, AN₁₀₀ (defined as a 25%, 50%, 75%, 90%, 100% reduction in the total AN count relative to Baseline)
- Flare (defined as a $\geq 25\%$ increase in AN count with an absolute increase in AN count of ≥ 2 relative to Week 16) by Week 48
- Time to flare from Weeks 0 to 16
- Time to flare from Week 16 to 48
- Absolute and percentage change (worst and average skin pain) from Baseline in HS Skin Pain score (11-point numeric rating scale)
- Skin pain response based on the threshold for clinically meaningful change (defined as at least a 3 point decrease from Baseline in HSSDD weekly worst skin pain score) among study participants with a score of ≥ 3 at Baseline
- Skin pain response (at least a 30% reduction and at least a 1-point reduction from Baseline in HSSDD weekly worst skin pain score [11-point numeric rating scale]) among study participants with a score of ≥ 3 at Baseline
- Skin pain response (at least a 30% reduction and at least a 1-point reduction from Baseline in HSSDD weekly average skin pain score [11-point numeric rating scale]) among study participants with a score of ≥ 3 at Baseline

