4.2.1.1 Handling missing data for the primary efficacy endpoint

If study participants have an intercurrent event as defined in Section 3.9, then the primary efficacy variable at that timepoint and all subsequent timepoints (whether the data were observed or not) will be set to “nonresponse” as the study participant has not met the criteria for response based on the composite estimand defined in Section 8.2. All remaining missing data for the endpoint will be imputed using multiple imputation Markov-Chain Monte Carlo method (MI-MCMC)/monotone regression for the primary analysis.

In addition, sensitivity analyses using NRI, MI-MCMC/reference-based methods, tipping point analysis, and observed case (OC) methods will be performed, which will assess the impact of different methods of handling missing data.

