8.4 Other efficacy endpoints

The other efficacy endpoints are listed below and will be evaluated according to the planned assessments in the protocol. This excludes the timepoints for the primary and secondary endpoints specified above in Section 8.2.1 and Section 8.3.

Missing data handling for these endpoints is described in Section 4.2.1.3.

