8.4.3 Flare relative to Baseline

See Section 8.3.2 for the derivation of flare.

Disease flare status will be summarized by treatment group and visit using frequencies and percentages. The denominator for the percentage calculations will be the number of participants with non-missing data in each treatment group. This summary will also include the number of participants with any flare in the Initial Period, Maintenance Period, and the combined Initial and Maintenance Period. A bar chart of percentage of participants with flare, by visit and treatment, will be presented.

In addition, for each participant, the number of flares during the Initial Treatment Period will be calculated and summarized by treatment group. A corresponding histogram summarizing the number of flares during the Initial Treatment Period will be presented.

8.4.4 Time to flare by Week 16

See Section 8.3.2 for the derivation of flare.

Time to flare (in days) during the Initial Treatment Period will each be calculated as:

Min (Date of first flare, Date of Week 16 visit) – Date of first dose of study medication + 1.
All visits in the Initial Treatment Period including unscheduled visits are considered.

Participants who discontinue study treatment without experiencing a flare prior to Week 16 Visit will be censored at the date of last lesion count assessment. Participants who reach the Week 16 Visit without experiencing a flare will be censored at the date of the Week 16 Visit. Participants who experience an intercurrent event prior to experiencing a flare will be treated as experiencing a flare at the date of the intercurrent event. Participants will be censored at Baseline if there is no Baseline lesion count assessment or no Post-Baseline lesion count assessment.

Time to flare will be estimated and presented using the Kaplan-Meier product-limit method for each treatment group.

Kaplan-Meier plots of time to flare will be presented by treatment group. In these Kaplan-Meier plots, the line will start at 0 and will increase over time, representing time to achieving the response.

The median time to flare, including the 2-sided 95% confidence interval, will be calculated for each treatment. Comparisons of bimekizumab vs placebo will be analyzed using a log-rank test stratified by Hurley Stage at Baseline and Baseline antibiotic use.

8.4.5 Time to flare by Week 48

See Section 8.3.2 for the derivation of flare relative to Baseline.

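### The non-missing denominators for AN count of 0, 1, or 2 (8.4.2.2) and by-visit flare (8.4.3) conflict with the SAP's own imputation rule, and after Week 32 they would tend to favour treatment

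*SAP*

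**What the plan says.** Section 2.2.1.3 lists "AN count of 0, 1, or 2" among the other efficacy endpoints. By-visit flare relative to Baseline is specified in 8.4.3, under the same heading of other efficacy endpoints. The opening of Section 8.4 applies one rule to everything below it: "Missing data handling for these endpoints is described in Section 4.2.1.3".

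Section 4.2.1.3 then states: "For other binary efficacy endpoints, missing data will be imputed using the same method as the primary efficacy endpoint". For the primary endpoint, Section 4.2.1.1 sets nonresponse from an intercurrent event onward, and adds: "All remaining missing data for the endpoint will be imputed using multiple imputation Markov-Chain Monte Carlo method (MI-MCMC)/monotone regression for the primary analysis".

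Two table footnotes support that rule. Table 4-1 footnote d confines NRI and observed-case results for other responder endpoints to the HiSCR50, 75, 90 and 100 summaries. Table 4-2 footnote a says that endpoints depending on lesion counts are derived from the imputed counts.

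Against this, 8.4.2.2 sets the denominator as "the number of participants in each treatment group in the RS with non-missing data at each visit", and 8.4.3 says: "The denominator for the percentage calculations will be the number of participants with non-missing data in each treatment group".

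Note a to Figure 2-1 (Section 2.3.1) reads: "Study participant should discontinue from the study from Week 32 on if no partial response is achieved", with partial response defined as at least 25% improvement in AN count from Baseline.

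**The concern.** If the two denominator sentences are followed, these summaries are observed-case although the general rule calls for composite handling plus multiple imputation. A programmer has to choose between two instructions.

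The choice matters most late in the Maintenance Treatment Period. The exit rule acts on AN count, and both summaries are built from AN count. Participants doing badly on the outcome drop out of the denominator, and the percentages for those who remain look better. The late AN 0/1/2 and flare tables would also not be comparable with the imputed HiSCR tables beside them.

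**Working it through.** No figure in the SAP depends on these denominators, so there is nothing to reproduce. The check has two parts.

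**1. Which rule governs?**

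| Place in SAP | Handling |
|---|---|
| 8.4, opening | all endpoints below go to 4.2.1.3 |
| 4.2.1.3 with 4.2.1.1 | failure after an intercurrent event, otherwise MI |
| Table 4-1, footnote d | NRI/OC only for HiSCR50/75/90/100 |
| Table 4-2, footnote a | imputed lesion counts feed the derived endpoints |
| 4.8 | flare subgroup summaries by visit, on imputed data as appropriate |
| 8.4.2.3 (AN25 to AN100) | no non-missing denominator, so 4.2.1.3 applies |
| 8.4.5 (time to flare by Week 48) | intercurrent event counts as flare |
| 8.4.2.2 and 8.4.3 | participants with non-missing data only |

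The last row stands alone. Within 8.4.2, AN100 follows the imputation rule while AN 0/1/2 just above it does not. Overall and subgroup flare tables could likewise follow different rules.

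**2. Direction and possible size after Week 32**

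*Direction.* A participant without a 25% reduction has an AN count above 0.75 × Baseline. To have an AN count of 2 or less as well, Baseline must be below 2/0.75 = 2.67, that is 2 or less. Apart from participants with so low a Baseline, those who meet the exit criterion do not have AN 0/1/2 at that time. In the other direction, flare needs at least a 25% increase, so anyone in flare at a visit is not a partial responder then. Removing these participants tends to raise the AN 0/1/2 percentage and lower the flare percentage.

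*Size, AN 0/1/2.* Let r be the rate on the full Randomized Set, d the share that has left, and q the rate among leavers under the 4.2.1.3 rule. The observed-case percentage is (r − dq)/(1 − d). It is largest at q = 0, where it equals r/(1 − d). Take r = 40% (assumed) in an arm of 140 (Section 2.4), so 56 participants have AN 0/1/2:

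| d (assumed) | with data | shown | excess, points |
|---|---|---|---|
| 5% | 133 | 56/133 = 42.1% | 2.1 |
| 10% | 126 | 56/126 = 44.4% | 4.4 |
| 15% | 119 | 56/119 = 47.1% | 7.1 |
| 20% | 112 | 56/112 = 50.0% | 10.0 |

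Over the same range of d, the excess is 1.6 to 7.5 points at r = 30% and 2.6 to 12.5 points at r = 50%.

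*Size, flare.* With rate f among those who stay and every leaver counted as flare, the full-set rate is (1 − d)f + d. The Table 2-1 planning values of 9% and 19% (flare by Week 16, used here only as placeholders for a late-visit rate) give:

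- f = 9%: 0.95 × 0.09 + 0.05 = 13.6% at d = 5%, and 0.80 × 0.09 + 0.20 = 27.2% at d = 20%.
- f = 19%: 0.95 × 0.19 + 0.05 = 23.1% at d = 5%, and 0.80 × 0.19 + 0.20 = 35.2% at d = 20%.

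These are also worst cases. If leavers flared at the same rate as those who stay, the difference would be zero.

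**The case against.** The best defence is that the specific text restates a general default. Section 3.1 bases efficacy percentages on participants with observed data and displays the denominator, so a shrinking late denominator would be visible. Section 8.4.7 uses similar wording without an observed-case label, so the missing label in 8.4.2.2 and 8.4.3 proves little, even though 8.4.1.6 and 8.4.6 do name observed-case handling. The Section 3.1 default applies only where nothing else is specified, however, and 4.2.1.3 with Table 4-1 does specify otherwise. The visible denominator stands as a mitigation.

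A second defence is that, given Table 4-2 footnote a, non-missing could mean non-missing after imputation. The bias would then largely vanish, but the restriction would do almost nothing and the text would still need clarifying.

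Third, much of the information appears elsewhere: by-visit HiSCR three ways (8.4.1.1), AN percentage change observed and imputed (8.4.2.1), and time to flare by Week 48 with intercurrent events as flare (8.4.5). That stands, and it limits what is lost.

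Fourth, the arithmetic assumes every leaver is a failure. Section 4.2.1.3 sets failure only after an intercurrent event, and the SAP does not say that a Week 32 exit is recorded as lack of efficacy. Other exits would be imputed. This stands too, so r/(1 − d) is an upper bound and not an estimate.

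**Conclusion.** The conflict is real, and the denominator sentences should yield to 4.2.1.3. As written, they would tend to overstate AN 0/1/2 and understate flare at visits after Week 32. The size cannot be computed from the SAP. The illustration of 42% to 50% in place of 40% rests on an assumed true rate, assumed exit of 5% to 20%, and no leaver achieving AN 0/1/2.

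A reader might infer more than the document supports:

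- *That non-responders as a class are removed.* The exit rule concerns lack of a partial response; someone with a 30% reduction is not a HiSCR50 responder but stays.
- *That the Week 32 visit is already distorted.* Participants may still be assessed at Week 32 before leaving, so the argument holds for later visits.
- *That both percentages are inflated.* The flare percentage is lowered; only the impression is more favourable in both cases.
- *That efficacy conclusions are at risk.* Flare by Week 16 keeps composite and MI handling (8.3.2, Table 8-2). AN 0/1/2 is not among the nominal tests in 8.5, and flare by Week 12, which is, follows the primary method. From Week 16 the placebo arm receives bimekizumab, so no placebo-controlled contrast exists at these visits.

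This is a worthwhile but minor correction to descriptive summaries.

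**What to change.** In both 8.4.2.2 and 8.4.3, replace the denominator sentence with: *intercurrent events and missing data handled as in Section 4.2.1.3, using the imputed lesion counts; denominator is all RS participants in the treatment group.* State that an intercurrent event counts as not achieving AN 0–2 in the first summary and as flare in the second.

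Keep the observed-case n/Nsub as a supplementary column and list that column as an OC exception in Table 4-1. Merely naming the two tables as OC exceptions would remove the contradiction but leave the outcome-dependent denominator after Week 32 in place.

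The cost is two sentences and one footnote. The imputed lesion counts are already planned.
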